3.3 Procedure

The study was conducted by two expert pediatric dentists. One of them gave all explanation, spoke with the children and carried out the anesthesia procedure and did the treatment procedure [name] and the other [name] was observing and assessing the children's pain perception.

In this study's cross-over design, children received both types of injections before filling/pulpotomy treatment on their maxillary primary molars in two separate appointments with a minimum interval of at least 1 week between procedures, on a side of the dental arch with the use of a needle free injection and on the other side with the traditional syringe. Type and sequence of administration to each individual were randomly assigned (using a coin). All dental equipment were introduced using 'tell-show-do technique. A total of 56 procedures were performed and divided into 2 groups according to the anesthesia technique. None of the children have undergone any previous dental local anesthetic experience, in order to be not influenced by a positive or negative memory.

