3.4 Data collection

A structured form was designed to collect information regarding

- (1) patient's age;
- (2) gender;
- (3) type of teeth injected
- (4) type of dental treatment (filling or pulpotomy);
- (5) total amount of local anesthetics (LAs) used (ml)
- (6) duration of the analgesia effect (min)
- (7) post-op pain (after one day)
- (8) score on WB PRS after injection
- (9) score on FLACC during injection.

The Effect of Needle-free Injection System on Dental Injection Pain in Children: A Cross-over, Randomized Clinical Trial

Statistical Analysis

Post hoc power analysis was conducted for the study and the results of the comparison between the injection systems and Wong Baker scores were evaluated. According to this, with a total data set of 28 individuals, consisting of two independent groups and two dependent measurements, the power of the study was found to be 0.94 according to the G*Power 3.9.1.4 program, based on the partial eta squared (η^2) value of 0.108 obtained with a 0.05 error margin from the repeated measures ANOVA. The data were statistically analyzed using SPSS software (version 15.0, SPSS). Paired t-tests or Wilcoxon nonparametric tests were used to compare data within groups over two time periods, according to check the distribution whether normally distributed or not. The Chi-square test (X^2 -test) was also used to compare discrete random variables. Spearman's Rho correlation coefficient was used to find any relationship between two continuous variables. A p-value ≤ 0.05 was considered statistically significant.

4. Results

Total of 28 children, consisting of 18 girls (64.3%) and 10 boys (35.7%) aged 6–12 years were involved in this study. Mean age was 8.07 years with a standard deviation of 1.41 years. At the end of this study, a total of 56 injections were obtained for 28 children as NF injection (n = 28) and TM injection (n = 28).

In the study, when the distributions of the parameters (gender, type of dental treatment, type of teeth, and post-operative pain) were evaluated according to the type of injection technique, it was found that there was no statistically significant difference between the groups. (Table 1)

Table 1. Distribution of injection techniques based on evaluation parameters

Variables		Needle Free (NF) n	Traditional Method (TM) n	Total	p
Gender	Girl	18	18	36	1,000
	Boy	10	10	20	
Type of dental treatment	Filling	22	14	36	0,051
	Pulpotomy	6	14	20	
Type of teeth injected	1 st primary molar	12	7	19	0,259

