	2 nd primary molar	16	21	37	
Post-op pain (after one day)	Pain	5	7	12	0,746
	No pain	23	21	44	

*The Chi-square test (X^2 -test) was also used to compare discrete random variables.

Accordingly Table 2, in the group that received Needle-Free anesthesia in the first session and Traditional Method in the second session, the Wong-Baker scores were 4.44 ± 3.28 and 1.55 ± 0.88 , respectively. On the other hand, in the group that received Traditional Method anesthesia in the first session, the WB score was 1.68 ± 1.91 , while in the Needle-Free anesthesia group, the WB score was 2.52 ± 2.56 . In both cases, regardless of the method of anesthesia applied first, no statistically significant difference was found in the two groups. In the FLACC scores, for the Traditional Method - Needle Free group significant change was observed ($p = 0.025$) while for the Needle Free- Traditional Method group no statistically significant difference was observed ($p=0.141$). There were significant differences in the Amount of Anesthetic Solution (ml) and Duration of the Analgesia Effect (min) between the first and second visits for both injection methods, respectively as $p=0.003$ for NF-TM and $p<0.0001$ for

The Effect of Needle-free Injection System on Dental Injection Pain in Children: A Cross-over, Randomized Clinical Trial

TM-NF groups. The amount of anesthetic solution used for the 1st visit NF injection was $0,91\pm 0,48$ ml and $0,65\pm 0,30$ ml was for the 2nd visit NF injection. These amounts were statistically lower than TM injection in both visits. In the first visit, the mean duration of the analgesia effect in the NF group was 85.00 ± 39.05 min, whereas in the second visit, the mean duration for NF injection was found to be 90.26 ± 43.25 min. In the TM group, the mean anesthesia duration for the first and second visits was 140.00 ± 59.97 min and 130.00 ± 50.74 min, respectively. Regardless of the visit in which it was first applied, the duration of the analgesia effect in the NF group was found to be statistically significantly shorter than in the TM group ($p < 0,001$).

Table 2: Comparison of the 1st visit and 2nd visit measurements for continuous random variables in Needle Free-Traditional Method and Traditional Method - Needle Free

	1 st visit	2 nd visit	p
Wong Baker (WB) Scores			
Needle Free-Traditional Method	4,44±3,28	1,55±0,88	0,056
Traditional Method - Needle Free	1,68±1,91	2,52±2,56	0,119
FLAAC			

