Needle Free-Traditional Method	0,78±1,09	0,11±0,33	0,141
Traditional Method - Needle Free	0,21±0,41	0,68±0,67	0,025
Amount of Anesthetic Solution (ml)			
Needle Free-Traditional Method	0,91±0,48	1,62±0,38	0,003
Traditional Method - Needle Free	1,37±0,42	0,65±0,30	<0,0001
Duration of the Analgesia Effect (min)			
Needle Free-Traditional Method	85,00±39,05	130,00±50,74	0,001
Traditional Method - Needle Free	140,00±59,97	90,26±43,25	<0,001

*paired t-test was used

*Needle Free-Traditional Method group: 1st visit Needle Free and 2nd visit Traditional Method was used of injection.

*Traditional Method - Needle Free group: 1st visit Traditional Method and 2nd visit Needle Free was used of injection

Table 3: Wong-Baker and FLACC Scores in Needle Free-Traditional Method and Traditional Method - Needle Free groups based on gender

	Gender	Needle Free-Traditional Method Group		p	Gender	Traditional Method-Needle Free Group		p
		1 st visit Needle Free	2 nd visit Traditional Method			1 st visit Traditional Method	2 nd visit Needle Free	
Wong Baker	Girl N=6	4.1, (1.5-8.5)	2, (0-2)	0,141	Girl N=12	2, (0.5-2)	1, (0-3.5)	0,558
	Boy N=3	4.1, (2-4)	2, (2-2)	0,18	Boy N=7	0, (0-4)	2, (2-4)	0,059
FLACC	Girl N=6	0, (0-1.5)	0, (0-0.25)	0,414	Girl N=12	0, (0-0)	0.5, (0-1)	0,053
	Boy N=3	1, (0-1)	0, (0-0)	0,180	Boy N=7	0, (0-1)	1, (0-1)	0,317

*Wilcoxon nonparametric test was used

*Needle Free-Traditional Method group: 1st visit Needle Free and 2nd visit Traditional Method was used for injection.

*Traditional Method - Needle Free group: 1st visit Traditional Method and 2nd visit Needle Free was used for injection

* The values are presented as Median, (Inter Quartile Range)

In our study, which used a crossover design, we evaluated the effect of gender differences on Wong-Baker and FLACC scores for needle-free and traditional method injections administered

The Effect of Needle-free Injection System on Dental Injection Pain in Children: A Cross-over, Randomized Clinical Trial

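### The cross-over is tested separately within each sequence (9 and 19 children), so technique is confounded with visit; combining the sequences makes the non-significant Wong-Baker result significant

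*Combined protocol and SAP*

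**What the plan says.** The Statistical Analysis section states: "Paired t-tests or Wilcoxon nonparametric tests were used to compare data within groups over two time periods". The significance rule is "A p-value ≤ 0.05 was considered statistically significant".

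Table 2 is titled as a "Comparison of the 1st visit and 2nd visit measurements for continuous random variables" and has one row per sequence for each outcome. Its footnote says "paired t-test was used". Table 3 gives the sequence sizes by gender: 6 + 3 = 9 children in NF-TM and 12 + 7 = 19 in TM-NF.

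For Wong-Baker, section 4 (Results) concludes: "In both cases, regardless of the method of anesthesia applied first, no statistically significant difference was found in the two groups". For FLACC it reports p = 0.141 in NF-TM and p = 0.025 in TM-NF.

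An analysis of all 28 children is mentioned once, as the source of the post hoc power figure of 0.94, which is "based on the partial eta squared (η^2) value of 0.108 obtained with a 0.05 error margin from the repeated measures ANOVA". The result of that ANOVA for technique is not given.

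**The concern.** In NF-TM, every child has NF at visit 1 and TM at visit 2. In TM-NF the order is the other way round. Inside either sequence, the visit contrast and the technique contrast are therefore the same contrast. If children score differently at a second visit for any reason, that shift adds to the technique effect in one sequence and subtracts from it in the other. A cross-over randomises sequence so that the two can be combined and the visit shift cancels. Testing the sequences separately gives that up.

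It also splits a small sample unevenly. Two p-values above 0.05 from 9 and 19 children are weak evidence of no difference, and weaker still when both differences point the same way. Injection pain is the subject of the trial's title, so the main result is at stake: a reader of section 4 would conclude that self-reported pain was not shown to differ between the techniques.

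**Working it through.** **Inputs.** Means, SDs and p-values are from Table 2; n is from Table 3. Write d for the mean of NF minus TM.

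| | NF-TM (n = 9) | TM-NF (n = 19) |
|---|---|---|
| Wong-Baker NF; TM | 4.44 ± 3.28; 1.55 ± 0.88 | 2.52 ± 2.56; 1.68 ± 1.91 |
| d | +2.89 | +0.84 |
| Reported p | 0.056 | 0.119 |
| FLACC NF; TM | 0.78 ± 1.09; 0.11 ± 0.33 | 0.68 ± 0.67; 0.21 ± 0.41 |
| d | +0.67 | +0.47 |
| Reported p | 0.141 | 0.025 |

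**Step 1: the plan's own power figure.** f² = 0.108/0.892 = 0.121. With 28 children, 2 measurements and an assumed correlation of 0.5 (the documents give none), λ = 0.121 × 28 × 2/(1 − 0.5) = 13.56. On 1 and 26 df the power is 0.943, matching the stated 0.94.

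**Step 2: SD of the within-child differences.** For a paired t-test, SD = |d|√n / t, where t is the two-sided quantile for the reported p on n − 1 df.
- Wong-Baker, NF-TM: t(8) = 2.23, so SD = 2.89 × 3/2.23 = 3.88.
- Wong-Baker, TM-NF: t(18) = 1.64, so SD = 0.84 × 4.36/1.64 = 2.24.
- FLACC: 1.23 and 0.84 by the same formula.

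The Wong-Baker SDs imply between-visit correlations of −0.61 and +0.53, which are feasible.

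**Step 3: technique effect, sequences combined.** Effect = (d₁ + d₂)/2. A visit shift enters d₁ and d₂ with opposite signs and cancels.
- Wong-Baker: (2.89 + 0.84)/2 = **+1.87**.
  - Pooled variance: (8 × 3.88² + 18 × 2.24²)/26 = 8.10, SD 2.85. SE = 0.5 × 2.85 × √(1/9 + 1/19) = 0.576. t(26) = 3.24, p = 0.003, 95% CI 0.68 to 3.05.
  - Unequal variances (Welch): SE = 0.5 × √(3.88²/9 + 2.24²/19) = 0.70, about 10.6 df, p = 0.022, 95% CI 0.33 to 3.40.
- FLACC: (0.67 + 0.47)/2 = **+0.57**.
  - Pooled: SE 0.197, t(26) = 2.89, p = 0.008, 95% CI 0.16 to 0.98.
  - Welch: p = 0.028, 95% CI 0.07 to 1.07.

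**Step 4: does the Wong-Baker result depend on the method?**
- Simple paired test on all 28, ignoring visit: (9 × 2.89 + 19 × 0.84)/28 = +1.50, p = 0.012.
- Visit 1 only, which carry-over cannot affect and which uses only printed means and SDs: 4.44 − 1.68 = +2.76, p = 0.009 (Welch 0.040).
- Rounding of the Table 2 entries moves the pooled p only between 0.0031 and 0.0034.
- Discarding the printed p-values and taking the largest difference SDs possible (correlation −1: 3.28 + 0.88 = 4.16 and 1.91 + 2.56 = 4.47): p = 0.045, pooled or Welch. The same extreme for FLACC gives 0.026 pooled and 0.053 Welch.

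**Step 5: power lost by splitting.** For a true difference of 1.87 with a difference SD of 2.84, power is 0.41 with 9 children, 0.77 with 19, and 0.88 combined. For a difference of 1.5 it is 0.29, 0.59 and 0.71.

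**Step 6: what the ANOVA figure of 0.108 measures.** From the same reconstruction, the visit effect is (0.84 − 2.89)/2 = −1.03, F = 3.17, partial η² = 3.17/(3.17 + 26) = 0.109. The technique effect (sequence-by-visit) has F = 3.24² = 10.5, partial η² = 0.287. The sequence effect has 0.054. The stated 0.108 matches visit, not technique.

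**The case against.** **The combined analysis may have been run.** The repeated-measures ANOVA has the right layout, with two groups and two measurements, and its group-by-visit term is the technique test. What can be said is that this result is not reported, not that nobody ever calculated it. At face value, the ANOVA figure even counts against the concern: the text ties 0.108 to the comparison of injection systems, and on 26 df that is F = 3.15, p = 0.088. Step 6 answers this, because 0.108 agrees with the reconstructed visit effect and is far from the technique effect. That is an inference, though a close numerical match.

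**Variances and scale.** The larger variance sits in the smaller sequence, where pooling understates the error, so the Welch figures are the safer ones to lead with. The scores are ordinal. Section 3.3.3 describes Wong-Baker as running from 0 to 5, but Table 4 shows a median of 7 and a quartile of 9.5, so the size of a point is unclear. A constant rescaling would leave the p-values unchanged.

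**Carry-over.** The implied sequence test for Wong-Baker gives p = 0.23, but it has little power. The visit-1 comparison is immune to carry-over and agrees.

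**Extent of the change.** NF is higher in both sequences as reported, so only the significance verdict changes, not the direction. The blanket non-significant statement covers Wong-Baker only; FLACC was already significant in one sequence. These points limit the wording and leave the defect in place.

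**Conclusion.** The concern holds. The reported analysis contains no estimate of the technique effect that is free of the visit effect and uses all 28 children. For Wong-Baker, supplying one moves the result from non-significant in both sequences to a significantly higher score with NF: +1.87, Welch 95% CI 0.33 to 3.40, p = 0.022 (pooled p = 0.003). FLACC moves from a split verdict to +0.57, Welch p = 0.028.

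These figures are reconstructed from summary statistics. They rest on the Table 2 p-values being two-sided paired t-tests and on sequence sizes of 9 and 19. The Wong-Baker result stays below 0.05 even when those p-values are ignored and the least favourable SDs are used. Patient-level data should supply the final numbers. The 0.94 power figure does not rescue the split tests: it refers to 28 children, and its effect size appears to be that of visit.

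**What to change.** - Replace the within-sequence tests with one cross-over analysis per outcome on all 28 children: technique, visit and sequence as fixed effects and child as random. Equivalently, compare the visit-1 minus visit-2 differences between the two sequences.
- Report NF minus TM with a 95% CI for each outcome, using a method that does not assume equal variances.
- For Wong-Baker and FLACC, add the rank-sum test of those differences between sequences.
- State which ANOVA effect the 0.108 belongs to, and report the technique term from that model.
- Reconcile the Wong-Baker range in section 3.3.3 with Table 4, so that the estimate has a defined unit.
- Rewrite Table 2 and the Wong-Baker and FLACC statements in section 4 from the patient-level result.

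The cost is a re-analysis of data already held and a revision of the Statistical Analysis section, Table 2 and the related results text. No further patients or measurements are needed.

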3.3.2 Injection with the traditional method (TM)

The TM was used with traditional syringe on the opposite side of the dental arch. The injection site was dried with a cotton-tip applicator, and topical anesthetic spray (Lidocaine 10%, Vemcain, Turkey) was applied to the injection area with cotton-tip for 1-2 min. The traditional injection was performed with a 26-gauge, 40-mm, disposable syringe with a needle (Genject, Turkey). The depth of penetration was only a few millimeters and 0.3ml of anesthetic solution was deposited. After 5 min the treatment commenced, and the children were instructed to raise their hand if they experienced pain during the procedure. Each time the child indicated pain, in accordance with the same protocol an additional 0.3 ml of anesthetic solution was administered, until the sufficient anesthetic effect was obtained and the final amount of anesthetic solution were recorded. Precautions were taken to prevent tissue ballooning. After the treatment, duration of the analgesia effect (min) were also recorded. The presence of post-operative pain in patients was assessed via a phone call 1 day after the procedure.

Both NF and TM anesthesia techniques were performed with 4% articaine hydrochloride with 1/100,00 epinephrine (Ultracaine D-S forte, Hoechst Canada Inc., Montreal Quebec, Canada) as an anesthetic agent.

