in different sequences over two sessions. The analysis showed no statistically significant differences between the groups (Table 3). Similarly, present study evaluated the impact of the type and sequence of restorations (filling-filling, filling-pulpotomy, pulpotomy -filling) on Wong-Baker and FLACC scores for needle-free and traditional method injections administered in different sequences over two sessions. Results demonstrated that there were no statistically significant differences between the groups (Table 4).

Table 4: Wong-Baker and FLACC Scores in Needle Free-Traditional Method and Traditional Method - Needle Free groups based on type of dental treatment

	Type of Dental Treatment	Needle Free-Traditional Method Group		p	Type of Dental Treatment	Traditional Method-Needle Free Group		p
		1 st visit Needle Free	2 nd visit Traditional Method			1 st visit Traditional Method	2 nd visit Needle Free	
Wong Baker	Filling-Filling N=4	7, (3-9.5)	2, (0.5-2)	0,109	Filling-Filling N=8	2, (0.5-2)	2, (0.5-5.5)	0,167
	Filling-Pulpotomy N=3	4, (2-4)	2, (0-2)	0,180	Filling-Pulpotomy N=2	0, (0-0)	1, (0-1)	0,317
	Pulpotomy-Filling N=2	1, (0-1)	2, (2-2)	0,317	Pulpotomy-Filling N=9	2, (0-3)	2, (0-4)	0,655
FLACC	Filling-Filling N=4	0.5, (0-2.5)	0, (0-0)	0,180	Filling-Filling N=8	0, (0-0)	1, (0-1)	0,096
	Filling-Pulpotomy N=3	1, (0-1)	0, (0-0)	0,180	Filling-Pulpotomy N=2	0, (0-0)	0.5, (0-0.5)	0,317
	Pulpotomy-Filling N=2	0, (0-0)	0.5, (0-0.5)	0,317	Pulpotomy-Filling N=9	0, (0-1)	1, (0-1)	0,257

*Wilcoxon nonparametric test was used

*Needle Free-Traditional Method group: 1st visit Needle Free and 2nd visit Traditional Method was used for injection.

*Traditional Method - Needle Free group: 1st visit Traditional Method and 2nd visit Needle Free was used for injection

*The values are presented as Median, (Inter Quartile Range)

*filling-filling group: 1st visit filling and 2nd visit filling restoration have been done

*filling-pulpotomy group: 1st visit filling and 2nd visit pulpotomy restoration have been done

*pulpotomy-filling group: 1st visit pulpotomy and 2nd visit filling restoration have been done

Table 5. Amount of Anesthetic Solution (ml) in Needle Free-Traditional Method and Traditional Method - Needle Free groups based on type of dental treatment

	Type of Dental Treatment	Needle Free-Traditional Method Group		p	Type of Dental Treatment	Traditional Method-Needle Free Group		p

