		1 st visit Needle Free	2 nd visit Traditional Method			1 st visit Traditional Method	2 nd visit Needle Free	
Amount of Anesthetic Solution (ml)	Filling-Filling N=4	0.65, (0.325-1.125)	1.3, (1.05-1.85)	0,068	Filling-Filling N=8	1.1, (1-1.85)	0.55, (0.325-0.9)	0,012
	Filling-Pulpotomy N=3	0.9, (0.3-0.9)	2, (1.5-2)	0,180	Filling-Pulpotomy N=2	1.4, (1.3-1.4)	1, (1-1)	0,180
	Pulpotomy-Filling N=2	1.35, (1.2-1.35)	1.75, (1.5-1.75)	0,180	Pulpotomy-Filling N=9	1.5, (1.1-1.85)	0.6, (0.3-0.9)	0,008

*Wilcoxon nonparametric test was used

*Needle Free-Traditional Method group: 1st visit Needle Free and 2nd visit Traditional Method was used for injection.

*Traditional Method - Needle Free group: 1st visit Traditional Method and 2nd visit Needle Free was used for injection

*The values are presented as Median, (Inter Quartile Range)

*filling-filling group: 1st visit filling and 2nd visit filling restoration have been done

*filling-pulpotomy group: 1st visit filling and 2nd visit pulpotomy restoration have been done

*pulpotomy-filling group: 1st visit pulpotomy and 2nd visit filling restoration have been done

Table 5 showed the evaluation whether the type and sequence of different restorations administered in different sequences over two sessions with needle-free and traditional method

10.04.2017

The Effect of Needle-free Injection System on Dental Injection Pain in Children: A Cross-over, Randomized Clinical Trial

injections resulted in any differences in the amount of anesthetic solution used. The results indicated a significant difference in the amount of anesthetic solution used in the group that received TM injection in the first session and NF injection in the second session, the group that received filling in both the first and second sessions, and the group that received pulpotomy in the first session and filling in the second session. A significantly lower amount of anesthetic solution was used in the NF injection in both groups (Table 5).

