According to Spearman's Rho correlation coefficient test, no correlation was found between age and Wong Baker, FLACC scores, and the amount of anesthetic solution administered respectively ($p=0,830$, $p=0,436$, $p=0,976$). Similarly, no correlation was found between Wong Baker scores and the amount of anesthetic solution administered ($p=0,537$) and Wong Baker scores and the duration of the analgesia effect ($p=0,468$). However, a negative correlation was found between the FLACC score and the amount of anesthetic solution ($p=0,033$). Moreover a positive correlation was found between the FLACC score and Wong Baker scores as well as between the amount of dose administered and duration of analgesia effect respectively ($p=0,000$, $p=0,009$).

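### Table 1 tests 56 paired injections as if independent, and the NF-TM dose and duration estimates are not adjusted for a pulpotomy imbalance (14 TM versus 6 NF visits) on which Tables 1 and 4 disagree

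*Combined protocol and SAP*

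**What the plan says.** Section 3.3 (Procedure) makes the data paired: "children received both types of injections before filling/pulpotomy treatment on their maxillary primary molars in two separate appointments", one technique per side. For categorical variables the Statistical Analysis section names one method: "The Chi-square test (X^2 -test) was also used to compare discrete random variables". No paired categorical test is named.

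Section 4 (Results) applies it to gender, treatment type, tooth type and post-operative pain by technique, and concludes: "it was found that there was no statistically significant difference between the groups. (Table 1". The treatment-type row shows 22 fillings and 6 pulpotomies for NF, 14 and 14 for TM, p=0.051.

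Table 4 and its text use three categories only, "type and sequence of restorations (filling-filling, filling-pulpotomy, pulpotomy -filling", with no pulpotomy-pulpotomy row. Table 5 splits dose by the same categories and concludes: "A significantly lower amount of anesthetic solution was used in the NF injection in both groups (Table 5". Table 2 compares dose and duration by paired t-tests within sequence, with no term for treatment type. For duration the text states that "the duration of the analgesia effect in the NF group was found to be statistically significantly shorter than in the TM group".

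Dose was not fixed. Under both techniques (3.3.1 and 3.3.2): "Each time the child indicated pain, in accordance with the same protocol an additional 0.3 ml of anesthetic solution was administered". The closing paragraph of the Results gives Spearman p-values without rho or n, for example "a negative correlation was found between the FLACC score and the amount of anesthetic solution".

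**The concern.** Table 1 counts every child twice; 28 children appear as 36 girls and 20 boys. A chi-square for independent groups ignores the pairing. For gender the comparison has no content, because the two columns hold the same children.

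The larger issue is what the treatment-type row shows. Half of the TM visits were pulpotomies, against about a fifth of the NF visits. If a pulpotomy draws more pain signals than a filling, it draws more top-ups, so the TM dose rises for a reason unrelated to technique; duration may follow dose. Calling this no difference on the strength of p=0.051 hides it. The tables that could show its effect also disagree on how many pulpotomies there were.

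At stake is the size of two reported NF effects, dose and duration. Wong-Baker and FLACC refer to the injection, before treatment starts, so the main pain comparison is outside this point.

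**Working it through.** **1. Reproduce Table 1.** For 22/6 versus 14/14 the expected counts are 18 and 10 per column, and each cell is off by 4.
- Pearson: 4² × (2/18 + 2/10) = 4.98, p=0.026.
- Continuity-corrected: 3.5² × (2/18 + 2/10) = 3.81, p=0.0509. This is the printed 0.051.
- Fisher: p=0.0496.

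Tooth type (0.259, corrected or Fisher) and post-operative pain (0.746, Fisher) also reproduce as unpaired tests on 56 injections.

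**2. Paired tests.** Exact McNemar uses only children whose two visits differ: p = 2 × P(X ≤ smaller count), X ~ Binomial(b+c, ½).
- Treatment type, Table 4 pairs (12 pulpotomy on TM only, 4 on NF only): 2 × 2517/65536 = 0.077.
- Treatment type, Table 1 margins, with k children having pulpotomy at both visits (b=14−k, c=6−k, k=0 to 6): 0.115, 0.096, 0.077, 0.057, 0.039, 0.021, 0.008.
- Post-operative pain, every possible pairing: 0.50 to 0.77.
- Tooth type, every possible pairing: 0.06 to 0.36.

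**3. Tables 1 and 4 side by side (pulpotomies).**

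| Source | NF | TM | Net TM excess |
|---|---|---|---|
| Table 1 | 6 | 14 | 8 |
| Table 4, NF-TM sequence (9 children) | 2 | 3 | 1 |
| Table 4, TM-NF sequence (19 children) | 2 | 9 | 7 |
| Table 4, total | 4 | 12 | 8 |

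The totals differ by two on each technique, but the net excess is 8 of 28 either way. By Table 4, 2+9=11 pulpotomies fell at visit 1 and 3+2=5 at visit 2, so procedure is also mixed with visit order.

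**4. Dose.** Let x = (pulpotomy at NF visit) − (pulpotomy at TM visit). Its mean is −8/28 = −0.286 under either table, so the crude NF−TM difference carries 0.286 times the pulpotomy effect. Differences of Table 5 medians:

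| Sequence | x | n | NF−TM (ml) |
|---|---|---|---|
| NF-TM | 0 | 4 | −0.65 |
| NF-TM | −1 | 3 | −1.10 |
| NF-TM | +1 | 2 | −0.40 |
| TM-NF | 0 | 8 | −0.55 |
| TM-NF | +1 | 2 | −0.40 |
| TM-NF | −1 | 9 | −0.90 |

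- Crude weighted mean: −0.714.
- Weighted regression on x: intercept −0.629, slope 0.298 (check: −0.629 − 0.286 × 0.298 = −0.714). 12% smaller.
- Adding sequence (the period term): −0.647, against −0.722 with sequences weighted equally. 10% smaller.
- Filling-filling children only: (4 × −0.65 + 8 × −0.55)/12 = −0.583. 18% smaller.

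**5. Duration.** From Table 2: (9 × −45.00 + 19 × −49.74)/28 = −48.2 min. The documents give no pulpotomy effect on duration. Assuming 10 to 60 min, the estimate moves from −48.2 to between −45 and −31 min. Removing the difference would need 48.2/0.286 = 169 min.

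**6. Correlations.** If all 56 injections were pooled, a technique difference in both variables produces a correlation by itself, equal to the product of their correlations with technique. From Table 2 means and SDs these are: dose −0.675, FLACC 0.395, duration −0.445, Wong-Baker 0.309.

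| Pair | Induced r | \|r\| implied by reported p, n=56 | n=28 |
|---|---|---|---|
| FLACC and dose | −0.27 | 0.29 (p=0.033) | 0.40 |
| Dose and duration | +0.30 | 0.35 (p=0.009) | 0.48 |

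For FLACC and Wong-Baker the induced r is only 0.12, so that correlation is not in question.

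**The case against.** The strongest reply is that little changes. On the pairs that Table 4 shows, exact McNemar leaves treatment type non-significant, and tooth type and post-operative pain stay so under any pairing. That stands, and it is why this point does not rest on significance.

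Second, technique and sequence were assigned by coin and eligibility required similar operative difficulty on both sides, so the excess may be chance and the crude estimate unbiased over randomisation. As a statement about the procedure that is fair. The estimate from this sample still carries the imbalance, and by Table 4, 16 of 28 children had different procedures on the two sides.

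Third, Table 5 already stratifies dose, and NF is lower in all six strata. Direction is therefore secure. What is missing is one adjusted estimate; four of the six strata hold 2 to 4 children.

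Fourth, the shrinkage is uncertain. Table 2 gives −0.71 ml in the nearly balanced NF-TM sequence and −0.72 in the imbalanced TM-NF sequence, which with no period effect implies almost no change (about −0.71). The same reasoning gives about 18 min per pulpotomy and −43 min for duration. But two sequence means cannot separate period from procedure, and for dose this reading ignores the gradient across Table 5, which has the same order within each sequence. The uncertainty is real and only the child-level data can settle it.

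Finally, the correlation argument is conditional on n=56 and uses Pearson arithmetic against Spearman tests. Both limits are accepted.

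**Conclusion.** The point holds. Three parts are certain from the documents: Table 1 uses unpaired tests on paired data; Tables 1 and 4 disagree on the number of pulpotomies (6 and 14 versus 4 and 12); and duration is neither stratified nor adjusted by treatment type.

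The sizes are less certain. The dose saving is about 10 to 18% smaller after allowing for procedure. This is a rough guide because it uses differences of medians and some strata of 2 or 3 children. The duration shift of 2.9 min per 10 min of pulpotomy effect rests on an assumed effect and an assumed sign. The correlation point depends on whether the 56 injections were pooled.

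The direction of the dose result and the post-operative pain conclusion do not change, and no plausible pulpotomy effect would remove the duration difference.

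**What to change.** 1. Reconcile Tables 1, 4 and 5 against the data forms first. Two pulpotomy-pulpotomy children listed as filling-filling would explain the gap exactly and leave the discordant counts at 12 and 4, but this is a hypothesis to check.
2. Show treatment type, tooth type and post-operative pain as paired counts with exact McNemar tests. Drop the gender test. State the net imbalance of 8 of 28 children in place of a statement of no difference.
3. For dose and duration, fit a cross-over model with technique, period, child and treatment type, and report the adjusted NF−TM difference with its confidence interval. Repeat it in the confirmed filling-filling children as a sensitivity analysis.
4. Report each correlation with rho and n, computed within technique or on within-child NF−TM differences. Withdraw the FLACC-dose and dose-duration findings if they vanish.

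The cost is a check of the forms and a re-analysis of collected data. Treatment type is already item 4 on the form (section 3.4) and uses about one degree of freedom. The reported dose saving will probably be somewhat smaller.
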